[figure not shown]

Evaluation of Metabolomic Biomarkers in Pulmonary Fibrosis

Study Protocol and Statistical Plan

We designed a single-center, prospective, cross-sectional investigation involving patients diagnosed with Pulmonary Fibrosis. Participants are recruited from the Interstitial Lung and Rare Diseases Outpatient Clinic at the Vanvitelli Respiratory Diseases Clinic, Monaldi Hospital, Naples, Italy. Patients were included if they met the following criteria: 1) Confirmed IPF diagnosis based on the 2018 ATS/ERS/JRS/ALAT guidelines [PMID: 30168753] within the past five years 2) diagnosis of other fibrotic interstitial lung disease different from IPF 3) age \geq 40 years, 4) ability to provide informed consent. Exclusion criteria included: 1) a current diagnosis of asthma or chronic obstructive pulmonary disease (COPD), 2) an acute Pulmonary Fibrosis exacerbation within the past three months. Demographic and anthropometric data—including sex, smoking history, and comorbidities—are systematically recorded. All participants undergo pulmonary function testing, including spirometry, body plethysmography, and single-breath diffusing capacity of the lungs for carbon monoxide (DLCO), following the 2022 ATS/ERS guidelines [PMID: 34949706]. Tests are performed using the Vynntus BODY system (Vyaire Medical), and the following parameters were measured: FEV₁, FEV₁%, FVC, FVC%, FEV₁/FVC, TLC, TLC%, RV, RV%, DLCO, and DLCO% [PMID: 22743675, PMID: 28893868]. Additionally, arterial blood gas (ABG) analysis was conducted to assess pH, partial pressure of oxygen (pO₂), partial pressure of carbon dioxide (pCO₂), bicarbonate (HCO₃⁻), and lactate levels. Functional capacity is evaluated using the 6-minute walk test (6MWT), performed according to ATS guidelines [PMID: 12091180]. The Gender-Age-Physiology (GAP) index was calculated to stratify IPF patients into three risk stages based on clinical (sex, age) and physiological (FVC, DLCO) parameters, providing an estimate of 1-, 2-, and 3-year mortality [PMID: 22586007]. To enhance prognostic accuracy, the Distance-Oxygen-Gender-Age-Physiology (DO-GAP) index was also determined by incorporating 6MWT distance and exertional hypoxemia [PMID: 37228268].

Study Protocol Design

Statistical plan

Baseline population characteristics, comparing the control group and Pulmonary Fibrosis patients. In particular, the χ^2 test or Spearman's rank correlation (Rho) was applied to categorical variables according to their distribution, while the Wilcoxon-Mann-Whitney test was used for continuous variables to identify significant differences between the two groups (controls and PF). For univariate correlations, Pearson's or Spearman coefficient are used as appropriate. These statistical methods provide a comprehensive understanding of the clinical and biochemical differences between the two groups and the relationships among the fatty acids studied. Finally, we evaluated the diagnostic potential of significant FAs for IPF using Receiver Operating Characteristic (ROC) curves. A p -value < 0.05 was considered statistically significant.

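### Treatment is not named among the recorded data and enters no analysis, so any treatment effect on fatty acids could not be separated from a disease effect

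*Combined protocol and SAP*

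**What the plan says.** The opening section of the protocol (Study Protocol and Statistical Plan) recruits from a specialist outpatient clinic. One inclusion criterion is "Confirmed IPF diagnosis based on the 2018 ATS/ERS/JRS/ALAT guidelines [PMID: 30168753] within the past five years". The next is "diagnosis of other fibrotic interstitial lung disease different from IPF", with no time limit. The exclusions are asthma or COPD and "an acute Pulmonary Fibrosis exacerbation within the past three months"; neither concerns treatment.

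On data collection the same section describes the background data as "including sex, smoking history, and comorbidities". Lung function, blood gases, the 6-minute walk test, GAP and DO-GAP are then described. Treatment and time since diagnosis are not mentioned.

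The Statistical plan compares controls with PF patients by χ² or Spearman for categorical variables and by Wilcoxon-Mann-Whitney for continuous ones. It adds univariate correlations and ends with ROC curves: "we evaluated the diagnostic potential of significant FAs for IPF". It contains no multivariable model, stratification, restriction or sensitivity analysis.

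**The concern.** The entry criteria allow patients who have been under care for some time, and some of these may be on treatment directed at their lung disease. Such treatment would probably be rare or absent among controls, although the documents do not define the controls. Treatment and case status would then largely coincide, and a controls-versus-PF test could not tell one from the other. Lipid-lowering treatment raises a related question, since its use may differ between groups.

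What is at stake is the final claim. A diagnostic marker is needed before the diagnosis is made, which is usually before disease-directed treatment has begun. A fatty acid that differs from controls only because patients are treated would have no value there. Only significant fatty acids go forward to the ROC step, so a treatment-driven marker that reaches significance is carried into the diagnostic conclusion. If treatment is not recorded at the visit, the problem cannot be examined reliably afterwards.

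**Working it through.** The documents state no sample size, effect size, SD or treated share, so there is no figure of theirs to reproduce. The check has two parts.

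**1. Can the plan separate treatment from disease?**

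- Eligibility: nothing restricts enrolment to untreated patients.
- Data: treatment is not named. The word *including* leaves open that it is recorded.
- Analysis: the group tests, the correlations and the ROC curves carry no covariate and no subset.

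So even if treatment is recorded, no planned step uses it. This part rests on the text alone.

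**2. How large could the effect be?**

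All inputs are assumptions: 50 per group; a normally distributed fatty acid with SD 1 and no relation to fibrosis; a share p of cases treated and no controls treated; treatment shifts the level by d SD. Then

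AUC = p × Φ(d/√2) + (1 − p) × 0.5.

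The chance that a two-sided Wilcoxon-Mann-Whitney test gives p < 0.05 was simulated (4,000 runs per scenario).

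| p | d | Φ(d/√2) | AUC from treatment alone | Chance of p < 0.05 |
|---|---|---|---|---|
| any | 0 | 0.500 | 0.50 | about 5% |
| 0.50 | 0.2 | 0.556 | 0.53 | about 8% |
| 0.30 | 0.5 | 0.638 | 0.54 | about 12% |
| 0.60 | 0.5 | 0.638 | 0.58 | about 30% |
| 0.75 | 0.5 | 0.638 | 0.60 | about 43% |
| 0.90 | 0.8 | 0.714 | 0.69 | about 93% |
| 0.60 | 1.0 | 0.760 | 0.66 | about 79% |
| 0.80 | 1.0 | 0.760 | 0.71 | about 96% |

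First and last non-null rows worked out: 0.50 × 0.556 + 0.50 × 0.5 = 0.528, and 0.80 × 0.760 + 0.20 × 0.5 = 0.708.

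The group size matters for significance but not for the AUC. At p = 0.75 and d = 0.5 the chance is about 28% with 30 per group and about 73% with 100 per group.

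**Bias in the other direction.** Suppose disease raises a real marker by 0.8 SD and treatment lowers it by 0.5 SD in 75% of cases. Untreated patients have AUC Φ(0.8/√2) = 0.714. The mixed case group has 0.75 × Φ(0.3/√2) + 0.25 × 0.714 = 0.75 × 0.584 + 0.25 × 0.714 = 0.617. A useful marker would look weaker than it is.

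**The case against.** The strongest objection is that the causal link lies outside the documents. They do not say how many patients are treated, with what, whether any treatment alters fatty acids, which specimen is assayed or who the controls are. This stands. It means that the size and direction of any bias cannot be derived, and every row of the table is conditional.

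A second objection is that the list of recorded data is plainly not complete. It omits age, which both the inclusion criteria and GAP need, and it names no anthropometric variable. Treatment may be recorded without being named, and the study-design figure is not available to read. This also stands. A reader might infer that the study fails to collect treatment; the documents support only that treatment is not named. The point survives because no analysis uses treatment in either case.

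Third, the five-year limit is a maximum and also admits newly diagnosed patients, so the case group need not consist of long-treated patients. That is correct, and it is what makes an untreated subset possible.

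Fourth, small effects matter little: at d = 0.2 and 50 per group, with 50% to 90% treated, the AUC is 0.53 to 0.55 and the chance of significance about 8% to 14%. An AUC near 0.7 needs most patients treated and a shift of about 0.8 to 1 SD. This is a fair limit on the concern.

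**Conclusion.** The concern holds in a conditional form. If disease-directed treatment affects fatty acids, the plan as written could not separate that effect from disease, and the AUC could be too high or too low. Under the assumptions set out above, the AUC produced by treatment alone runs from about 0.53 to 0.71, with a chance of significance from about 8% to 96%. The actual size is unknown.

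A reader might go further and infer that treatment effects will be reported as disease markers, or that the AUC will be inflated. The documents do not support either: they show neither that treatment shifts any fatty acid nor in which direction. This is a low-cost improvement that could change the diagnostic conclusion, not a demonstrated error in the results.

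**What to change.** Record at sampling: antifibrotic, corticosteroid or immunosuppressant, and lipid-lowering treatment; and time since diagnosis. Then add to the Statistical plan:

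- **(a)** Repeat the controls-versus-PF comparison and the AUC, with 95% confidence intervals, in patients not on disease-directed treatment.
- **(b)** For each significant fatty acid, compare treated with untreated patients within the PF group, adjusting for diagnosis (IPF or other ILD), a recorded severity measure (FVC% or DLCO%) and time since diagnosis. Without this adjustment the comparison would mix treatment with disease type and stage.
- **(c)** As a sensitivity analysis, add a regression of each significant fatty acid on group with lipid-lowering treatment as a covariate. The plan has no adjusted model now, so this is a new one. The same approach would not work for disease-directed treatment if no control receives it, which is why (a) uses restriction.

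Report the untreated-subset AUC beside the main AUC. Where the untreated result does not support the main one, or is too imprecise to judge, limit the diagnostic conclusion to treated, established disease. Avoid a pass rule based on results of roughly similar size, unless a threshold is fixed in advance.

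The cost is a few chart fields and one sensitivity table; no clinical management changes. The downside is precision. For a marker with no true difference, the standard error of the AUC is √[(n₁ + n₂ + 1)/(12 n₁ n₂)]. With 50 controls and 50 cases this is √(101/30,000) = 0.058, a 95% half-width of about 0.11. If 80% of 50 cases are treated, 10 remain: √(61/6,000) = 0.101, a half-width of about 0.20. At 50% treated, 25 remain: √(76/15,000) = 0.071, about 0.14. The subset may therefore be unable to confirm a marker, and the report should say so where this happens.

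### The fatty-acid screen names no adjustment for age, sex or smoking, so an imbalance between patients and controls could send a fatty acid unrelated to fibrosis to the ROC step

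*Combined protocol and SAP*

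**What the plan says.** The Statistical plan opens with "Baseline population characteristics, comparing the control group and Pulmonary Fibrosis patients". It gives chi-square or Spearman for categorical variables, and for the rest it states that "the Wilcoxon-Mann-Whitney test was used for continuous variables to identify significant differences between the two groups (controls and PF". Associations are examined by univariate correlations. The methods together are said to "provide a comprehensive understanding of the clinical and biochemical differences between the two groups and the relationships among the fatty acids studied". The last analysis step is "we evaluated the diagnostic potential of significant FAs for IPF using Receiver Operating Characteristic (ROC) curves", with significance at p < 0.05. No regression, stratification or matching is named in the available text.

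The opening design section says "Participants are recruited from the Interstitial Lung and Rare Diseases Outpatient Clinic" and sets eligibility for patients, who include those with a "diagnosis of other fibrotic interstitial lung disease different from IPF". It does not say who the controls are. Demographic data are recorded, "including sex, smoking history, and comorbidities". Age appears as an eligibility criterion and in the GAP index, which stratifies IPF patients "based on clinical (sex, age) and physiological (FVC, DLCO) parameters". None of these variables is given a role as a covariate.

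**The concern.** PF patients and controls are not randomised groups. If they differ in age, sex or smoking, and an FA varies with one of these, the FA will differ between the groups even if it has nothing to do with fibrosis. An unadjusted test cannot separate the two explanations, and a larger sample makes the false selection more likely. Testing baseline characteristics may reveal the imbalance, but it does not remove it from the FA comparison. At stake is whether an FA put forward as a diagnostic candidate reflects fibrosis or only who was enrolled as a control.

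**Working it through.** **Is the FA screen unadjusted?** The Wilcoxon-Mann-Whitney sentence follows the words on baseline characteristics and does not name FAs, so applying it to them is an inference. It is the natural one: the plan says these methods cover biochemical differences between the groups, and no other two-group test for a continuous variable is named that could make an FA significant. If significance refers instead to the univariate correlations, those are unadjusted too.

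**Inputs.** The documents give alpha = 0.05 and state no sample size, effect size or AUC, so there is no planned figure to reproduce. Assumed: a two-sided test; n = 30, 50 or 100 per group; one confounder shifted by d = 0, 0.5 or 1 SD between groups; within-group correlation r = 0.3 with an FA that has no disease effect.

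**Selection rate.** The confounder shifts the FA by r·d SD. A normal approximation to the chance of selection is Φ(r·d·√(n/2) − 1.96). At d = 1:
- n = 30: Φ(1.162 − 1.96) = 0.212
- n = 50: Φ(1.500 − 1.96) = 0.323
- n = 100: Φ(2.121 − 1.96) = 0.564

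Simulation (40,000 runs per cell) of the Mann-Whitney test, against a linear model on inverse-normal ranks with group and confounder:

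| Gap d | Mann-Whitney, n = 30 / 50 / 100 | Adjusted, n = 30 / 50 / 100 |
|---|---|---|
| 0 | 4.8% / 5.0% / 4.9% | 5.0% / 5.0% / 5.0% |
| 0.5 SD | 8.1% / 11.2% / 17.6% | 5.0% / 4.9% / 4.9% |
| 1 SD | 19.7% / 30.3% / 54.0% | 5.2% / 5.1% / 5.0% |

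If the confounder is measured with reliability 0.8, the adjusted rates in the six cells with a gap are 5.2-7.0%. Adjustment then reduces the problem without fully removing it.

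**Precision.** The adjusted/unadjusted SE ratio has two parts. Collinearity with group contributes √(1 + d²/4), and the variance explained by the confounder contributes √(1 − r²) = √0.91 = 0.954. In large samples:
- d = 0: 0.954 × 1 = 0.954
- d = 0.5: 0.954 × 1.031 = 0.983
- d = 1: 0.954 × 1.118 = 1.067

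At these sample sizes the ratios are about 0.96, 0.99 and 1.07-1.08. With no gap and 30 per group, power for a true 0.6 SD difference is 60% by Mann-Whitney and 65% adjusted.

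**AUC of an unrelated FA.** Its expected unadjusted AUC is Φ(r·d/√2). At d = 1 this is Φ(0.212) = 0.584. Taking the larger of AUC and 1 − AUC, the mean before any selection is about 0.58-0.60. Among FAs that pass the adjusted screen it is 0.65, 0.62 and 0.59. Selecting and evaluating on the same data therefore adds about 0.06, 0.03 and 0.01. The rest is confounding left in an unadjusted AUC, plus folding at 0.5 in small samples.

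**AUC of a related FA.** Take a true 0.6 SD effect and d = 1. The adjusted AUC is about Φ(0.6/(0.954·√2)) = Φ(0.445) = 0.67. If confounding acts with the disease effect, the unadjusted AUC is Φ(0.9/√2) = 0.74. If it acts against it, the unadjusted AUC is Φ(0.3/√2) = 0.58. Adjustment can therefore lower or raise the AUC.

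**The case against.** The strongest reply is that nothing shows an imbalance. The documents give no sample size, age or smoking gap, or FA-confounder correlation, and the illustration runs from no problem at all to 54%. The text favours no point in that range. This stands, so the point is a risk without a safeguard.

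A reader might go further and infer that the controls are unmatched, or that the FA results are biased. The documents do not support either. A figure is not shown and no text survives under Study Protocol Design, so control selection or matching may be described there. Matching on age and sex would leave mainly smoking, together with the need to keep the matching factors in the model.

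The ROC comparator for IPF is also unstated. If it is the patients with other fibrotic disease, the simulated PF-versus-control contrast describes the screening step and not the ROC contrast.

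Two further inferences fail. One is that adjustment must cost 3% or 12% in SE at the two gaps; that counts collinearity alone and omits the variance the covariate explains. The other is that AUCs of 0.65, 0.62 and 0.59 for unrelated FAs are mainly selection optimism; most of the excess over 0.5 is present before selection.

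Finally, regression is one remedy among several, and one simulated confounder does not show the cost of adjusting for three. Both remarks are fair. Neither supports leaving the screen with no adjustment.

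**Conclusion.** The point holds as a risk that should be fixed, with low to moderate confidence about its size. On the natural reading, and also on the alternative reading through correlations, the FA screen has no adjustment for age, sex or smoking. Under the assumed correlation and sample sizes, false selection of a confounded FA ranges from the nominal 5% with balanced groups to about one in two at a 1 SD gap with 100 per group. Adjustment for an exactly measured confounder restores about 5%. The conclusion rests on the FA screen being inferred, on the available text being silent about controls and matching, and on a single linear confounder standing in for all three.

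**What to change.** - Make the main FA comparison a linear regression of each FA (log or inverse-normal rank scale) on group, age, sex and smoking, keeping any matching factors in the model. Report adjusted differences with 95% CIs and keep Mann-Whitney as descriptive.
- Select FAs for ROC on the adjusted result. Report a covariate-adjusted AUC beside the unadjusted one, with 95% CIs, and label both as apparent because the same data select and evaluate the FAs.
- State how controls are chosen and what the ROC comparator is. Check that the groups overlap on the covariates before relying on the model.
- Name in advance any comorbidity that enters a sensitivity model, since some may follow from the disease.

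**Cost.** SAP wording and a few more models, provided that age, sex and smoking are available for controls; if not, they must be collected. Precision falls modestly if the groups differ greatly on the covariates, and AUCs may fall or rise with the direction of confounding.

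### The only between-group comparison, controls versus PF, is unadjusted, and the visible text sets no eligibility, matching or covariate rule for the controls, so a fatty-acid difference could reflect age, sex or smoking

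*Combined protocol and SAP*

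**What the plan says.** The opening design paragraph of the combined protocol and SAP describes a "single-center, prospective, cross-sectional investigation involving patients diagnosed with Pulmonary Fibrosis". It gives one recruitment source: "Participants are recruited from the Interstitial Lung and Rare Diseases Outpatient Clinic". The inclusion list begins "Patients were included if they met the following criteria". Its disease criteria are confirmed IPF or "diagnosis of other fibrotic interstitial lung disease different from IPF"; these can only be alternatives, and both require fibrotic lung disease. An age limit of 40 years is in the same list. The exclusions that follow include "a current diagnosis of asthma or chronic obstructive pulmonary disease (COPD"). Sex, smoking history and comorbidities are recorded.

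Controls appear only under Statistical plan. Continuous variables are tested with Wilcoxon-Mann-Whitney "to identify significant differences between the two groups (controls and PF"); categorical variables get chi-square or Spearman's rank correlation. Fatty acids found significant are then assessed by ROC curves for IPF, with p < 0.05 as the threshold. The visible text says nothing about who the controls are, how many there are, where they come from, or whether they are matched to patients. It describes no covariate adjustment.

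**The concern.** A two-group comparison of a blood marker is informative about disease only if the groups are otherwise alike, or if the analysis allows for the ways they differ. Neither is provided for here. Patients are at least 40 and free of asthma and COPD; the text does not say the same of controls. If controls are younger, smoke less or have a different sex mix, any fatty acid related to those factors will differ between the groups even if fibrosis has no effect on it.

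The problem then passes to the diagnostic claim. The ROC step takes only the fatty acids that passed the unadjusted test, so a marker of age or smoking can be selected and given an AUC as though it were a marker of IPF. A larger sample does not help: the bias is fixed by how the controls differ, and more subjects only make it easier to detect.

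**Working it through.** **Reading the text.** Setting the design paragraph beside the Statistical plan gives the following.

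- Design paragraph: one source (the ILD clinic), two alternative disease criteria that both need fibrotic ILD, and an age limit and asthma/COPD exclusion given alongside them. Controls are not mentioned.
- Statistical plan: the only between-group comparison is controls versus PF, and every stated method (chi-square, rank test, univariate correlation, ROC) is unadjusted as described.

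So no stated design feature makes the groups alike, and no stated analysis corrects for their being unlike.

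**Size, by illustration.** The documents give no sample size, effect size, SD or expected AUC, so there is no figure of theirs to reproduce. All inputs below except the 0.05 level are assumptions.

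- No effect of fibrosis on the fatty acid.
- r: within-group correlation of the fatty acid with age, 0.1 to 0.4.
- D: age gap between the groups in within-group SDs, 0 to 2.
- n: 50 per group, with 30 and 100 as checks.
- Normal data; Wilcoxon-Mann-Whitney test, two-sided at 0.05 (the plan does not state sidedness).

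Formulas: spurious shift = r × D, in SDs of the fatty acid; AUC = Φ(r × D / √2). For example, r = 0.2 and D = 1 give a shift of 0.20 and AUC = Φ(0.141) = 0.556. Rejection rates come from 4,000 simulated studies per row.

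| r | D | Shift (SD) | AUC | Rejection rate, n = 50 per group |
|---|---|---|---|---|
| any | 0 | 0 | 0.500 | about 5% |
| 0.1 | 0.5 | 0.05 | 0.514 | 4.9% |
| 0.2 | 1 | 0.20 | 0.556 | 15.9% |
| 0.3 | 1 | 0.30 | 0.584 | 29.8% |
| 0.4 | 1 | 0.40 | 0.611 | 50.0% |
| 0.4 | 2 | 0.80 | 0.714 | 97.3% |

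Simulation error is small: for the fourth row, 1.96 × √(0.3 × 0.7 / 4,000) = 0.014, about 1.4 percentage points.

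**Effect of sample size.** For r = 0.2 and D = 1, the rates at 30, 50 and 100 per group are 12.0%, 15.9% and 27.9%. For r = 0.1 and D = 0.5 they are 6.2%, 4.9% and 6.2%, close to nominal throughout. False positives therefore rise with n when the groups differ materially, and there is little harm when they are well aligned.

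**The case against.** The strongest reply is that this is an omission, not a flaw in method. The inclusion list is expressly about patients, and a patient list that does not admit controls does not forbid a separately recruited control group, which the Statistical plan takes for granted. That stands. A reader might infer that the two parts of the document contradict each other, or that controls are exempt from the age limit and the asthma/COPD exclusion. The text supports neither inference. It is silent on control eligibility, and the exclusion sentence is not expressly confined to patients.

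Four further points also stand.

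- A figure is missing from our copy and the heading Study Protocol Design has no text beneath it, so a control arm may be drawn there.
- No primary or main comparison is named. Controls versus PF is simply the only between-group one, and it opens as a comparison of baseline characteristics.
- The ROC comparator is not stated. It could be controls or other fibrotic ILD, so the AUCs above describe the curve only if controls are the comparator. Selection of fatty acids from the controls-versus-PF test carries the problem forward in either case.
- The size rests on assumed values, and with closely aligned groups there is almost none.

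The baseline comparison is a partial safeguard: it could show an imbalance in sex or smoking, but no stated analysis would then correct for it. None of these points supplies a covariate rule for the comparison.

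**Conclusion.** The concern holds as a weakness in the stated analysis, joined to an undefined control group. Followed as written, the plan can attribute to fibrosis a fatty-acid difference that arises from age, sex or smoking, and can carry it into the ROC analysis. Under the assumed values at 50 per group, false-positive rates run from about 5% with well-aligned groups to about 97% with a strongly age-related fatty acid and a 2 SD age gap. Where this study falls in that range cannot be told from the documents, because they do not describe the controls. The conclusion does not depend on the missing figure: a drawn control arm might settle who the controls are, but the Statistical plan's tests would still be unadjusted. The change is one the sponsor should make; the text does not show that the results will be biased.

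**What to change.** 1. **Analysis.** Base the controls-versus-PF comparison of each fatty acid on a regression, on ranks or transformed values, adjusted for age, sex and smoking history. Keep the Wilcoxon-Mann-Whitney test as descriptive. Select fatty acids for the ROC step from the adjusted result. Name the ROC comparator (controls or other fibrotic ILD) and report a covariate-adjusted AUC.
2. **Controls.** State their source and number, that they have no fibrotic ILD, and that they meet the same age limit and asthma/COPD exclusion as the patients. Confirm that age, sex and smoking history are recorded for them.
3. **Alignment.** The protocol mixes past and present tense, so recruitment may be open or closed. If it is open, frequency-match controls to enrolled patients on age band, sex and smoking history. If it is closed, report the overlap of the groups on these variables and restrict the analysis to the region of overlap, since adjustment outside it is extrapolation.

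The cost is a protocol paragraph, slightly more analysis work, some loss of precision from adjustment or restriction, and possibly slower control recruitment. No new procedure is needed. Aligned controls without ILD will not show whether fatty acids separate IPF from other fibrotic ILD; if that is the diagnostic question, the named comparator must reflect it.

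### ROC curves are planned only for significant fatty acids, apparently screened in the same sample, so the AUCs reported for selected markers are too high on average

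*Combined protocol and SAP*

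**What the plan says.** Three sentences of the Statistical plan section form a chain. For continuous variables, "the Wilcoxon-Mann-Whitney test was used for continuous variables to identify significant differences between the two groups (controls and PF"). The threshold is that a p "value < 0.05 was considered statistically significant". Finally, "we evaluated the diagnostic potential of significant FAs for IPF using Receiver Operating Characteristic (ROC) curves".

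The number of markers is not given; the section refers only to "the relationships among the fatty acids studied". The design paragraph describes one sample: "We designed a single-center, prospective, cross-sectional investigation involving patients diagnosed with Pulmonary Fibrosis". The PF group is mixed, because the inclusion criteria also admit a "diagnosis of other fibrotic interstitial lung disease different from IPF".

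Neither part describes a second sample, cross-validation, optimism correction, multiplicity adjustment, a fixed direction for the AUC, or the comparator for the IPF ROC curves. Group sizes are not given. That the FAs are screened by the Mann-Whitney test in the same sample is not said outright, but no other dataset and no other between-group test for continuous variables is described.

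**The concern.** The last analysis in the plan is a statement about diagnostic potential, and only FAs that have already shown a difference reach it. If screen and ROC curve use the same patients, an FA enters the ROC results because its observed separation was large, and chance contributes to that. About 5% of truly useless FAs pass a 0.05 screen, and those that pass must show a respectable AUC. A reader would then see a short list of AUCs with no view of the FAs left out, and could hardly tell a useless FA from a weak one.

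A second difficulty sits inside the first. The screen contrasts controls with all PF, while the ROC analysis is for IPF against an unnamed comparator. How large the bias is, and which FAs it touches, depends on that comparator.

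**Working it through.** **Inputs.** From the plan: the Mann-Whitney screen of controls against PF, p < 0.05, ROC for significant FAs only, one sample, PF made up of IPF and other fibrotic ILD. Assumed, because not stated: two-sided test, equal groups of n = 20, 30, 50 or 100, normally distributed markers, and IPF as half of PF where the split matters. The plan states no AUC or sample size, so there is no figure of its own to reproduce.

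**Step 1: the screen is a threshold on the AUC.** AUC = U/(n1·n2). With n per group and no true difference, its standard error is √((2n+1)/(12n²)). A selected FA must therefore show an AUC, flipped above 0.5 if necessary, of at least about 0.5 + 1.96·√((2n+1)/(12n²)). For n = 20 this is 0.5 + 1.96·√(41/4800) = 0.68. For 30, 50 and 100 it is 0.65, 0.61 and 0.58.

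**Step 2: false selections.** Each null FA passes with probability of about 0.05. If 20 independent null FAs were tested (number assumed), 20 × 0.05 = 1.0 would be expected to pass, and the chance of at least one is 1 − 0.95²⁰ = 0.64.

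**Step 3: simulated mean AUC of selected FAs.** Markers were shifted by √2·z(true AUC), tested with continuity correction at 0.05, and the AUC flipped above 0.5. For the same-contrast rows there were at least 10,000 data sets per cell, with a Monte Carlo standard error of at most 0.001.

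| ROC contrast, true AUC | n = 20 | 30 | 50 | 100 |
|---|---|---|---|---|
| Same as screen, 0.50 | 0.71 | 0.68 | 0.64 | 0.60 |
| Same as screen, 0.60 | 0.73 | 0.69 | 0.65 | 0.62 |
| Same as screen, 0.70 | 0.75 | 0.73 | 0.71 | 0.70 |
| Same as screen, 0.80 | 0.81 | 0.80 | 0.80 | 0.80 |
| IPF vs controls, FA shifted in IPF only, 0.70 | 0.81 | 0.78 | 0.75 | 0.72 |
| IPF vs controls, FA shifted in IPF only, 0.80 | 0.86 | 0.84 | 0.82 | 0.80 |
| IPF vs controls plus other ILD, 0.50 | 0.65 | 0.62 | 0.59 | 0.57 |
| IPF vs other ILD, 0.50 | 0.60 | 0.59 | 0.57 | 0.55 |

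**Step 4: the role of flipping.** Without flipping, selected null FAs average 0.50, because they fall on both sides. At true 0.60 flipping hardly matters: the unflipped means after selection are 0.725, 0.691, 0.653 and 0.620. Flipping alone, with no selection, gives null FAs 0.574, 0.560, 0.546 and 0.533 on the screening contrast.

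**Step 5: why the mixed contrast is worse for strong FAs.** If half of PF is IPF and only IPF is shifted, a true IPF-vs-controls AUC of 0.80 becomes 0.5 × 0.80 + 0.5 × 0.50 = 0.65 in the screen. Such an FA passes only 36%, 52%, 77% and 97% of the time, so those that pass are a favourable subset.

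**Step 6: IPF against other ILD.** For a null FA the screen adds nothing here: without selection, flipping alone gives 0.606, 0.586, 0.566 and 0.546, in line with the last row of the table.

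**The case against.** The strongest defence is that the plan speaks only of diagnostic potential, promises no validated test or cut-off, and bases no decision on an AUC. ROC curves for markers that differ between groups are common as exploratory description. If confidence intervals were reported, they would show part of the weakness: on the screening contrast the median lower 95% bound of a selected null FA is 0.54, 0.53, 0.52 and 0.51 at the four sizes. This tempers the severity. It does not remove the bias, and the plan does not mention intervals.

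It is also fair that no size can be attached to this study. Every figure above rests on assumed group sizes, equal allocation and normal markers.

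Several stronger readings are tempting and should not be drawn:

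- A reader might infer that every reported AUC is materially inflated. On the screening contrast that is not so: at true 0.80 the bias is 0.01 or less.
- A reader might conversely infer that strong FAs are safe. That holds only if the ROC contrast equals the screen, and the plan's wording (PF in one place, IPF in the other) leaves this open.
- A reader might infer that comparing IPF with other fibrotic ILD avoids the problem. It removes the selection bias for a null FA, but flipping AUCs above 0.5 still lifts them.
- A reader might infer that a table of all FAs corrects the individual values. It does not: an FA that would have been selected keeps its estimate, apart from its direction label.

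**Conclusion.** The concern holds on the natural reading of the Statistical plan section, namely that screen and ROC curves use the same sample. The AUCs of selected FAs are then too high on average, most for null and weak FAs and in small groups. On the screening contrast, with AUCs flipped above 0.5, the bias for a null FA falls from about +0.21 at 20 per group to about +0.10 at 100. At true 0.60 it falls from about +0.13 to +0.02, whether or not AUCs are flipped. If the ROC is IPF vs controls and the FA differs only in IPF (half of PF, assumed), even a true 0.80 is overstated by about 0.06 at 20 per group, with almost nothing left at 100.

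These are scenarios, not estimates for this study. The point should be addressed, with medium confidence: the mechanism is arithmetic, but its size here cannot be known from the documents.

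**What to change.** In the Statistical plan section:

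- Replace significant FAs with all FAs measured, and report AUC with 95% CI for each.
- Name the ROC comparator for IPF: controls, other fibrotic ILD, or both.
- Fix the direction in advance, for example AUC as the chance that an IPF value exceeds a comparator value, allowed to fall below 0.5. Without this, a complete table would still lift null FAs.
- Label any FA highlighted for significance, or as the best, as exploratory. Do not present a bootstrap-corrected AUC for it as unbiased. In simulated selected null FAs, repeating the selection inside the bootstrap moved the mean only from 0.713 to 0.664 at 20 per group, and from 0.595 to 0.572 at 100, against a true 0.50.
- If a data-driven cut-off or a multi-FA panel is reported, derive it inside cross-validation or bootstrap and report the corrected performance.

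This removes the selective reporting and makes the set of AUCs unbiased as a whole: with direction fixed, null FAs average 0.500 at every size. It does not shrink the AUC of an FA that is then picked out, which is why the exploratory label is needed.

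The cost is a change of wording, with no new patients. The downside is a longer results table and a less favourable overall picture.
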